VIII. Protection of Human Research Participants-Computer Based Training

As per the UTMB institutional policy and guidelines, the study PIs and all members of the research team will successfully complete HIPAA and CITI Basic Course and Health Information Privacy & Security (HIPS) Training for Clinical Investigators.

The University of Massachusetts Amherst Institutional Review Board will approve this plan, with the project protocol, prior to implementation of the study.

STUDY TIME FRAME:

With a proposed study duration of 4 years, the timeline for allocating research efforts and expected objective accomplishments is as follows:

1. Preparatory period (0-6 months)

This period encompasses the time from grant notification to study initiation (approximately 6 months). During this period the following task will be accomplished:

- Obtain UTMB Institutional Review Board (IRB) approval for the study (timeframe 1-3 months);
- Finalize all necessary research agreements with the study's participating hospital sites;
- Construction of study specific Case Report Form (CRF);
- Design of study database to capture and process all collected study variables; *Milestone #1: IRB approval*

2. Study Enrollment Period (32 months)

This period encompasses the timeframe of the first 32 months from study initiation. This period's primary objective is to successfully enroll 30 eligible patients in the study. In case of slow accrual, specific measures (enhanced referral program, study advertisement, etc) will be taken. During this period the following study tasks are expected to be accomplished:

- Continuing enrollment of the eligible patients as study subjects;
- Preoperative (baseline) subject data collection;
- Preoperative patient management;
- Perform the Masquelet or the CTMC defect reconstruction surgery;
- Intraoperative data collection;
- Immediate and early postoperative data collection

Milestone #2: Enrollment of 30 eligible patients

Milestone #3: The Masquelet or CTMC defect reconstructive surgery

The recorded preoperative study variables will permit realization of the following study objectives:

- Determine the perioperative safety and efficacy of the Masquelet versus the CTMC defect reconstructive technique;
- Identify the specific indications for performing the Masquelet versus the CTMC technique among the enrolled subjects;
- Provide a thorough characterization of the patient population that presents with segmental bone defects that warrant surgical reconstruction (specific aim 1);
- Establish defect characteristics among the study subjects treated with the Masquelet versus the CTMC procedure (part of specific aim 2);
- Collect and analyze the distribution of patients within specific study arms (Option A vs Option B) (part of specific aim 3);
- Establish the cost or preoperative and surgical management of the study subjects;
- Provide an analysis of patients with segmental bone deficiency who did not meet study eligibility criteria;
 - Establish the extent of patient compliance with immediate and early postoperative regimen.

3. Study Follow-up Period (18 months)

This period encompasses the timeframe of the last 18 months, i.e. from termination of enrollment to study completion. This period's primary objective is to successfully complete follow-up of all enrolled patients. During this period the following study tasks are expected to be accomplished:

- Continuing postoperative data collection;
- Analysis of data collection process (consistency, redundancy, dropout rate);
- Tentative statistical analysis of the collected data;
- Establish costs of subject follow-up incurred;
- Itemize all resource expenditure for total treatment costs assessment.

Milestone #4: Follow-up completion of 30 study subjects

4. Study Post Completion Period (2-4 months)

This period encompasses the timeframe after the study has been terminated. The research efforts in this period include:

- Thorough analysis of all pre-, intra-, and postoperative variables collected in the study to accomplish the specific study aims 2, 3 and 4.
- Assessment of the safety and efficacy of the CTMC defect reconstructive technique
- Establishing the clinical indications and treatment recommendation for CTMC the based upon the treatment outcome;
- Assessment of the total resource expenditure related to the CTMC reconstruction technique (in accordance with the graft option type) and comparison with the standard defect reconstruction modalities (study specific aim 5);
- Data presentation at international/national research meetings.
- Manuscript preparation and submission to a high-impact-factor peer-reviewed journal.

Milestone #5: Data presentation in research forums

Milestone #6: Manuscript publication

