
Throughout the entire post-operative study period (18 months), the patient's status will be monitored for complications and adverse events. If a complication or adverse events occurs, they will be reviewed by the PIs, the study staff, and key personnel and reported to the UTMB IRB according to regulatory and institutional policies. In addition, the study documents will be monitored by the UTMB's Research Services, Monitoring and Quality Assurance department for Clinical Research at 3-month-intervals. For the duration of the study, the PIs will routinely meet with the study coordinating staff to discuss the study progress, review the enrolled patients, and discuss all complications and/or adverse events as they occur. At 6 month intervals the PIs will meet with the study's biostatistician to perform preliminary statistical analysis of the collected data. The investigators will use

these meetings to make adjustments in the course of the study in case of enrollment issues and/or other logistic problems occur.

Study Variables

All study preoperative, intraoperative and postoperative variables will be recorded to construct a database of patients presenting with segmental bone defects and treated with the Masquelet or the CTMC technique in combination of auto- or allograft.

Preoperative variables are defined as all the patients- and their health-related data that are collected prior to the Masquelet or the CTMC reconstructive procedure (to include surgeries performed prior to the first stage of the Masquelet or the index CTMC surgical procedure). Preoperative variables to be collected will include:

- Patient (baseline):
 - A) Demographics (age, gender, ethnicity; social functioning/background);
 - B) Overall health status;
 - C) Risk factors (tobacco, alcohol, recreational drugs);
 - D) Co-morbidities
 - E) Concomitant medications (past 60 days prior to enrollment)
 - F) Past (last 10 years) medical history
- Defect:
 - A) Etiology:
 - Traumatic: Systemic and specific extremity injury characteristics to include Injury Severity Score (ISS) (Baker 1974); Gustilo-Anderson classification (Gustilo 1976) for open fractures, gunshot injury characteristics, type of firearm, bullet/missile retention; nature and extent of blast injury, limb neurovascular status.
 - Iatrogenic: Specific diagnosis, details on disease (infection, tumor) course and history; type of nonunion (hyper-, oligo-, atrophic, septic).

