All these questionnaires have been validated as valuable outcome measure instruments. Furthermore, they are endorsed by the American Academy of Orthopaedic Surgeon as recommended reliable and valid tools in the assessment of musculoskeletal treatment outcome. The enrolled patients will complete the questionnaires at the initial, midcourse, and final follow-up visits. The time burden to complete the questionnaires is approximately 30 minutes.

Statistical Methodology

Descriptive statistics will be used to analyze the collected data specifically to:

- characterize the patient with segmental bone deficiency; □ estimate the proportion of healing with/without complications; □ cross-compare the recorded variables.

Paired Student t-test will be used to test the effects of the Masquelet versus the CTMC defect reconstruction on the outcome measures.

Analysis of covariance (ANCOVA) will be used for pair-wise comparison within the two treatment arms (graft Option A vs. Option B).

A mixed model for repeated measures will be conducted to evaluate:

- the effect of the Masquelet versus CTMC defect reconstruction on the outcome measures, adjusting for patient demographics and clinical characteristics;
- the effect of the specific defect characteristics (etiology, size, location, adjacent soft tissue involvement, etc) on the treatment outcome;
- the possible interaction effects between treatment and defect characteristics.

Multiple models will be used in case the proposed sample size would not have enough power to produce an accurate predictive model which accounts for all possible morbidities and interactions. Simple models using modern penalty function techniques (lasso, elastic net, boosted trees, etc.) to control model complexity should provide a useful initial predictive tool for each clinical and quality of life outcome.

Both receiver operating curve (ROC) analysis and clinical judgment will be used in determining the optimal clinical indications and timing for defect reconstitution with the definitive defect reconstruction using the Masquelet versus the CTMC technique.

Sample Size Justification

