Consideration for termination of the subject participation in the study after the subject has been enrolled and/or study end point includes:

- Intraoperative determination of need for surgical procedure outside the study scope or protocol;
- Identifying any valid exclusion criterion after the subject's enrollment;
- Secondary procedure disrupting or preventing implementation of either the Masquelet or the CTMC defect reconstruction technique as in the study protocol;
- Evidence of infection or neoplasm recurrence post defect reconstruction;
- Evidence of vascular compromise in the affected extremity resulting in secondary intervention affecting healing;
- Subject declines continued participation;
- Subject is non-compliant with follow up care and instructions;
- Termination for any reason deemed mandatory by the PIs;
- Defect is completely healed before the end of the follow-up (i.e., 24 months); □ Subject becomes pregnant before the defect reconstructive surgery; □ Subject completes the study.

Subject Recruitment

Patients who present to the UTMB hospital with a traumatic segmental defect or a medical condition (nonunion, infection, neoplasm) to be treated with segmental bone resection will be recruited either prior to or following hospital admission. The PI ([name]) will be notified by the admitting physician. The patient and his/her medical conditions will be reviewed in accordance with the study inclusion/exclusion criteria. If eligible, patients will be approached to discuss their participation in the study.

The study discussion will include an explanation of the study objectives; the voluntary nature of the research; study requirements and/or compliance; randomization into one of the study treatment arms, termination and end points; reviewing both the Masquelet and the CTMC surgical defect reconstructive procedures; the alternative defect treatment options; the selection of autogenous RIA-harvested bone graft or allogeneic bone in combination with DBM, the study risks and benefits, the confidentiality of the subject's information, medical records and study-related documents, the potential costs to the patient and/or the patients insurance (standard of care), the costs covered through study funding; the contact persons/agencies for questions.

Obtaining Signed Informed Consent

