Routine measures (standard of care) will be taken to minimize and/or eliminate risks to the study subjects. These risks will be monitored and mitigated in accordance to the subject's medical condition and the pre- and post-reconstruction medical interventions. Subjects will be routinely followed in the post defect reconstruction and beyond the study designated time points, if necessary (in case of ongoing adverse events or pregnancy).

As per a study inclusion criterion, eligible female patients must have a negative serum pregnancy test to be enrolled into the study. Female subjects enrolled in the study will be encouraged not to get pregnant throughout the entire study period (ie, 18 months). If subject pregnancy occurs, it will be documented. The subject will be advised to notify her obstetrical physician. If the resulting birth is abnormal, the abnormality will be reported as an adverse event.

If the subject sustains physical injury or contracts a disease because of any substance given or procedure performed due to participation in this study their injury will be treated. The subject's medical insurance will be billed and any charges not covered by the subject's insurance or health care program will be the subject's responsibility. In addition, the subject will be responsible for paying any costs related to illnesses and medical events that are not associated with participating in the study.

ADVERSE EVENTS:

The PIs and the members of the study research team are responsible for the detection and documentation of events defined as an adverse event (AE). The investigators are also responsible for appropriate documenting and reporting of all AEs.

AE monitoring will be conducted at all follow-up intervals (including also those intervals not mandated by the protocol).

AE is defined as any adverse event, whether or not that event is felt to be related, occurring at the time of study. AEs will be treated in accordance with accepted medical standards and documented in the subject's study record and monitored by the PIs and research team. AEs will be reported to the UTMB IRB and to the US Army Medical Research and Materiel Command's Office of Research Protections, Human Research Protections Office (HRPO).

All AEs will be assessed to determine the following:

- A) whether event meets the criteria for an AE;
- B) the relationship to study treatment;
- C) the severity of the event;
- D) the "expectedness" of the event.

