If the subject sustains physical injury or contracts a disease because of any substance given or procedure performed due to participation in this study their injury will be treated. The subject's medical insurance will be billed and any charges not covered by the subject's insurance or health care program will be the subject's responsibility. In addition, the subject will be responsible for paying any costs related to illnesses and medical events that are not associated with participating in the study.

V. Plan for Monitoring Safety/Confidentiality

The PI and co-PI (as listed above) will be responsible for monitoring the safety environment of the participants.

Conditions that would necessitate termination of the subject participation in the study after the subject has been enrolled and/or reach study end point include:

- intraoperative determination of need for surgical procedure outside the study scope or protocol;
- identifying any valid exclusion criterion after the subject's enrollment;
- secondary procedure disrupting or preventing implementation of either the Masquelet or the CTMC defect reconstruction technique as in the study protocol;
- evidence of infection or neoplasm recurrence post defect reconstruction;
- evidence of vascular compromise in the affected extremity resulting in secondary intervention affecting healing;
- subject declines continued participation;
- subject is non-compliant with follow up care and instructions;
- termination for any reason deemed mandatory by the PIs;
- defect is completely healed before the end of the follow-up (ie, 24 months);
- subject becomes pregnant before the defect reconstructive surgery;
- subject completes the study.

The PIs will be study medical monitor and they will ensure that:

- only subjects who meet the study eligibility criteria are enrolled.
- the informed consent process will be conducted appropriately and that informed consent will be obtained prior to proceeding with any study procedures. (any problems with the obtaining the informed consent .
- data will be collected and analyzed strictly as designated in the protocol.
- adverse events (AEs) will be reviewed promptly and reported as required (see Section VII below).

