NCT 02015390

**The Comparative Efficacy of the Masquelet versus Titanium Mesh Cage
Reconstruction Techniques for the Treatment of Large Long Bone Deficiencies**

PI: [name], PhD
[name]

The University of Texas Medical Branch; Galveston, TX

Jun 22, 2020

STATISTICAL PLAN AND DATA ANALYSIS:

Statistical Methodology

Descriptive statistics will be used to analyze the collected data specifically to:

- characterize the patient with segmental bone deficiency;
- estimate the proportion of healing with/without complications;
- cross-compare the recorded variables.

Paired Student t-test will be used to test the effects of the Masquelet versus the CTMC defect reconstruction on the outcome measures.

Analysis of covariance (ANCOVA) will be used for pair-wise comparison within the two treatment arms (graft Option A vs. Option B).

A mixed model for repeated measures will be conducted to evaluate:

- the effect of the Masquelet versus CTMC defect reconstruction on the outcome measures, adjusting for patient demographics and clinical characteristics;
- the effect of the specific defect characteristics (etiology, size, location, adjacent soft tissue involvement, etc) on the treatment outcome;
- the possible interaction effects between treatment and defect characteristics.

Multiple models will be used in case the proposed sample size would not have enough power to produce an accurate predictive model which accounts for all possible morbidities and interactions. Simple models using modern penalty function techniques (lasso, elastic net, boosted trees, etc.) to control model complexity should provide a useful initial predictive tool for each clinical and quality of life outcome.

Both receiver operating curve (ROC) analysis and clinical judgment will be used in determining the optimal clinical indications and timing for defect reconstitution with the definitive defect reconstruction using the Masquelet versus the CTMC technique.

Sample Size Justification

Based on the data from the PIs' preliminary clinical series of 20 patients, it can be assumed that 75% of patients with segmental bone defects reconstructed with the CTMC technique will heal without complications. In the present study we propose to enroll and follow-up 30 patients throughout 4 years of the clinical trial duration.

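### Treatment outcomes are also grounds for leaving the study, and no rule covers outcome data after exit or censoring

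*Protocol*

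**What the plan says.** The exit list appears twice in the protocol with the same entries but different force. Study Termination or End Point introduces it with "Consideration for termination of the subject participation in the study after the subject has been enrolled and/or study end point includes". Section V of the data and safety monitoring plan introduces it with "Conditions that would necessitate termination of the subject participation in the study after the subject has been enrolled and/or reach study end point include". Among the entries are "Evidence of infection or neoplasm recurrence post defect reconstruction", vascular compromise that leads to a secondary intervention affecting healing, and "Defect is completely healed before the end of the follow-up (i.e., 24 months". The 24 months in that last entry conflicts with the 18 months given under Study Variables (postoperative variables), Study Follow-up and the monitoring plan's Study Design.

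Some text points towards keeping subjects under observation:

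- Course of Action: "Throughout the entire post-operative study period (18 months), the patient's status will be monitored for complications and adverse events".
- Risk Management and Emergency Response provides for follow-up "beyond the study designated time points, if necessary (in case of ongoing adverse events or pregnancy".
- Resources Expenditure and Cost-Effectiveness Analysis names an intent-to-treat analysis, without defining it.
- Study Time Frame sets completed follow-up of all 30 subjects as a milestone.

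The analyses that depend on the missing rule are the log-rank and proportional hazards comparisons of healing and functional recovery (protocol, Resources Expenditure and Cost-Effectiveness Analysis) and the repeated-measures model (SAP, Statistical Methodology: "A mixed model for repeated measures will be conducted to evaluate"). The SAP names no time-to-event analysis. Neither document has a censoring, competing-event or missing-data rule.

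**The concern.** Recurrence, vascular compromise and healing can all be consequences of the reconstruction technique. If they also end participation, the subjects with missing later data are selected by how they fared. Two problems could follow.

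(a) A subject who leaves unhealed after recurrence or vascular compromise and is then censored is treated as having the same prospect of healing as those who stay. The healing curve is then too high.

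(b) A subject who leaves on healing gives no later function, quality-of-life, QALY, cost or CT data. Those still observed late are increasingly the ones who did not heal.

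Where the arms differ in failure rate or speed of healing, either mechanism could distort the comparison. Data never collected cannot be recovered at analysis.

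**Working it through.** **Step 1. What each analysis loses if participation and collection both stop at exit.**

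| Analysis | Exit at recurrence or vascular compromise | Exit at complete healing |
|---|---|---|
| Proportion healing without complications | None: already a failure | None: status known, apart from later complications |
| Complications (chi-square) | Little, for events seen before exit | Later complications only |
| Time to healing (log-rank, proportional hazards) | Overstated if censored | None: healing is the event |
| Function, questionnaires, cost | Later values lost | Later values lost |
| 12-month CT; QALY at 12 and 18 months | Lost if exit is earlier | Lost if exit is earlier |

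The plan gives no exit rates, so every rate below is assumed. The one rate it supplies is 75% uncomplicated healing for the CTMC technique (Sample Size Justification). It gives none for the Masquelet arm.

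**Step 2. Part (a), one arm.** Let q be the share who exit for failure, hU healing among the others, and hF healing among those who exit, had they been followed. True healing = (1 − q)hU + q·hF. A curve that censors the exits estimates hU. Overstatement = q(hU − hF).

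- The 75% limits q. Uncomplicated healing cannot exceed (1 − q)hU, so with hU = 0.85, q can be at most 1 − 0.75/0.85 = 0.118 in the CTMC arm. A share of 20% would give at most 0.80 × 0.85 = 0.68, and 30% caps it at 0.70 whatever hU is. Neither is used here.
- With q = 0.10, hU = 0.85, hF = 0.30: true healing = 0.90 × 0.85 + 0.10 × 0.30 = 0.795. The censored curve shows about 0.85, an overstatement of 5.5 points (3.5 to 7.5 for hF from 0.50 to 0.10).
- Between arms with the same hU and hF, the hidden difference is (difference in q) × (hU − hF). For 10% vs 5% it is 0.05 × 0.55 = 2.75 points; for equal q it is zero.

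**Step 3. Part (b), amount lost.** Apply 75% healing to both arms. If 20% to 50% of healers are healed by month 6, then 30 × 0.75 × 0.20 = 4.5 to 30 × 0.75 × 0.50 = 11.25 of 30 subjects leave before the scheduled CT and before any postoperative QALY value.

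**Step 4. Part (b), between arms.** Let p = 0.75 heal in both arms, f be the share of healers healed by month 12, and D = 20 points the function gap between healed and unhealed. There is no true difference between arms. The share of an arm still observed at month 18 is 1 − pf. Never-healers are (1 − p)/(1 − pf) of those.

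- f = 0.80: 0.40 × 15 = 6 remain, of whom 0.25/0.40 = 62.5% never healed.
- f = 0.50: 0.625 × 15 = 9.4 remain, of whom 0.25/0.625 = 40% never healed.
- Bias = 20 × (0.625 − 0.40) = 4.5 points against the faster-healing arm.
- f = 0.70 vs 0.60: 20 × (0.25/0.475 − 0.25/0.55) = 20 × 0.072 = 1.4 points.

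A large simulation of a mixed model (visits at months 3, 6, 12 and 18; between-subject SD 12, residual SD 8; healed by month 6: 50% vs 20% of healers, or 40% vs 30% in the milder case) leaves about 2.2 and about 0.6 to 0.7 points respectively. Omitting month 3 reduces the 2.2 to about 0.6 to 0.7.

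**Step 5. Scale.** For healing of 0.795 vs 0.8225 (the 10% vs 5% case) at 15 per arm, the 95% half-width is 1.96 × √(0.795 × 0.205/15 + 0.8225 × 0.1775/15) = 0.28, or 28 points. For function, total SD = √(144 + 64) = 14.4. The half-width is 1.96 × 14.4 × √(2/15) = 10.3 points at 15 per arm and 1.96 × 14.4 × √(1/6 + 1/9.4) = 14.8 with 6 and 9.4 remaining. Every bias above is smaller than its half-width.

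**The case against.** The case on the other side is substantial, and much of it stands.

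- **Uncomplicated healing is safe.** It is the only outcome with a stated rate, and a subject with recurrence or vascular compromise has already failed it. This stands. The concern is confined to the time-to-healing analysis and to late outcomes.
- **Stopping collection is not written down.** The documents end participation; that data collection ends too is inferred. Follow-up visits and the 12-month CT are described as routine, so some post-exit data may exist. This stands, but neither document says the study would use them.
- **Retention language exists.** The 18-month monitoring covers complications and adverse events, the extension beyond schedule applies only where necessary, and intent-to-treat cannot supply values that were not collected. None of this settles the handling of healing, function or questionnaire data.
- **The infection entry is ambiguous.** It may mean only recurrence of an infection present at entry, which would reduce the number of exits.
- **Exit at healing may not be prompt.** Defect Healing Assessment makes final status depend on several readers, so part (b) may be smaller than shown.
- **The mixed model helps.** It roughly halves the part (b) bias in the illustration, more if month 3 is left out, but does not remove it.

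A reader might also infer that QALY timing is contradictory, because Questionnaires says "The enrolled patients will complete the questionnaires at the initial, midcourse, and final follow-up visits". It is not: the procedure table has QALY preoperatively and at months 12 and 18, which fits that description.

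**Conclusion.** Three things are established from the text: the two exit lists differ in force, the listed events feed the planned comparisons, and no rule covers post-exit outcome data or censoring. The consequence is conditional. If the mandatory wording governs and collection stops at exit, missing data depend on outcome. Time-to-healing is then overstated where failures are censored, and late data are lost for early healers.

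A reader might go further and infer that the trial's comparison is biased for or against the CTMC arm. The documents do not support that. They give no exit rates by arm, so neither the size nor the direction can be computed, and with equal failure rates and healing speed the bias between arms is zero. The protocol's expectation of shorter treatment time with CTMC is not a rate. The figures of 1.4 to 4.5 points (about 0.6 to 2.2 in a mixed model) and 2.75 points on healing are illustrations from assumed inputs, and all lie below sampling error. The point should be fixed because the loss is avoidable and cheap to prevent, not because a material bias has been shown. Confidence is medium.

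**What to change.** - Reconcile Study Termination or End Point with section V of the monitoring plan in one wording that separates the end of protocol treatment from the end of data collection.
- For every randomized subject who has not withdrawn consent, continue outcome data collection on the existing procedure table to month 18 after any listed event. Clinical care is unchanged.
- State in the SAP that recurrence and vascular compromise are not non-informative censoring in the time-to-healing analysis. Either follow healing status through the event, or treat the event as a failure or competing event. Both are defensible; choose in advance.
- Say whether the infection entry covers new infection or only recurrence.
- Reconcile the 24 months in the exit entry on healing, in both lists, with the 18 months stated elsewhere.

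The cost is a protocol amendment, a short SAP addition, and some additional visits and data entry for healed or failed subjects. Visits to month 18 are already scheduled and reimbursed.
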